#### **2.1.1.4 Discharge from hospital**

Discharge from hospital is not time point specific visit and will be mapped based on the actual day since day 1 if the discharge is on or before Day 29. For the assessments that are scheduled on every other day and discharge falls on a day without scheduled assessment, the discharge visit will be mapped to next scheduled visit for the corresponding assessment.

#### **2.1.1.5 Unscheduled visits**

Data collected at unscheduled visits will not be used for analysis by visit, but will be included in analyses based on all post-baseline values such as Last observation carried forward (LOCF) imputation or summary of abnormal findings during the study.

#### **2.1.1.6 Nominal visit of discharge/Day 29**

To evaluate the treatment effect at the time of discharge up to Day 29, summary at discharge/Day 29 may be provided based on assessments from

- early discharge visit for those who are discharged from hospital before Day 29 or
- from last available assessment up to Day 29 if not discharged before Day 29

#### **2.1.1.7 Missing and imputable dates**

The general approach to handling missing dates is described in [Section 5.1](#).

#### **2.1.1.8 Laboratory results meeting limits of quantification**

For observations beyond the limits of quantification, a value of the lower limit of quantification (LLOQ) or the upper limit of quantification (ULOQ) will be used for analysis if not otherwise specified. This rule will be applied to all applicable laboratory values prior to checking against the notable criteria as well as computation of any statistics.

### **2.2 Analysis sets**

The **Full Analysis Set (FAS)** comprises all participants to whom study treatment has been assigned by randomization. An accidental or premature randomization of a patient without providing study medication is considered as a misrandomized patient. Misrandomized patients will be included in FAS. According to the intent to treat (ITT) principle, participants will be analyzed according to the treatment they have been assigned during the randomization procedure.

The FAS will be used for the summary of demography and baseline characteristics as well as for all efficacy analyses.

The **Safety Set** includes all participants who received at least one dose of study treatment. Participants will be analyzed according to the study treatment received, where treatment

received is defined as the actual treatment if the participant took a treatment different from the assigned treatment.

The Safety Set will be used in the analysis of all safety variables.

Rule of exclusion criteria of analysis sets is provided in [Section 5.4](#).

### 2.2.1 Subgroup of interest

Subgroup analyses will be conducted to assess consistency of the treatment effect among the subgroups without multiplicity adjustments. The following subgroups will be evaluated for the primary endpoint, i.e. survival without ever requiring invasive mechanical ventilation from Day 3 (inclusive) up to Day 29 (inclusive).

- Age category (< 65, ≥ 65 years)
- Age category (12 - <18; 18 - <40; 40 - <65; 65 - <75; ≥75)
- Baseline clinical status based on 9-point ordinal scale (≤4, ≥5)
- Baseline body Weight (40 kg - <60 kg, 60 kg – 80 kg, >80 kg)
- Baseline BMI categories (≤ 30.0 kg/m^2 and > 30.0 kg/m^2)
- Sex (male, female)
- Race (White, Asian, Black, other)
- Ethnicity: Hispanic, non-Hispanic
- Region (North America, Russia, Rest of Europe)
- Active comorbidities based on Medical History
  - Cerebrovascular disease (Yes, No)
  - Chronic heart disease (Yes, No)
  - Hypertension (Yes, No)
  - Diabetes (Yes, No)
  - Asthma (Yes, No)
  - COPD (Yes, No)
  - Chronic kidney disease (Yes, No)
  - Malignant neoplasm (Yes, No)
  - Liver disease (Yes, No)

- Use of dexamethasone >= 6 mg/day or equivalent or not (Yes, No)
- Use of remdesivir or not (Yes, No)
- Use of convalescent plasma/serum or not (Yes, No)
- Use of hydroxychloroquine or not (Yes, No)
- Use of azithromycin or not (Yes, No)
- Use of JAK inhibitor or not (Yes, No)
- Use of Heparin or not (Yes, No)

- Use of anti-IL6 treatment (Yes, No)

The subgroups based on the use of prior COVID-19-induced pneumonia treatment medication are defined as with/without the given medication that started on or after the onset of the first symptom of COVID-19-induced pneumonia and before the study treatment date (or randomization date if no study treatment is taken).

## **2.3 Patient disposition, demographics and other baseline characteristics**

No inferential testing on the differences in patient disposition, demographics and other baseline characteristics between treatment arms will be performed.

### **2.3.1 Patient disposition**

The number and percentage of patients who were screened but not randomized will be summarized based on all screened patients.

The following disposition status will be summarized based on the FAS:

- The number and percentage of patients who receive study treatment
- The number and percentage of patients who discontinue from study as well as the primary reason for discontinuation on or prior to Day 29
- The number and percentage of patients who discontinue from study as well as the primary reason for discontinuation on or prior to the time of data cut for Day 29 DBL or EoS (for the final DBL)
- The number and percentage of patients who are ongoing up to the time of data cut for Day 29 DBL. This is only applicable for the analysis based on Day 29 DBL

The number of patients included in each analysis set will be tabulated. Patients exclusion from analysis sets will be listed for all patients with reasons for exclusion (i.e. including both protocol and non-protocol deviations).

### **2.3.2 Demographic characteristics**

Demographic characteristics, including gender, race, ethnicity, age, age categories (<18, 18-  
<65, 65-<75 and ≥ 75 years), body weight, body categories (40 to <60 kg, 60 to 80 kg, >80 kg),  
body mass index (BMI), BMI categories ( $\leq 30.0 \text{ kg/m}^2$  and  $> 30.0 \text{ kg/m}^2$ ), country and region  
(North America vs. Europe) will be summarized with descriptive statistics for the FAS by  
treatment and overall.

### **2.3.3 Baseline disease characteristics**

The summary of the following baseline disease characteristics will be provided by treatment group using the FAS:

- Days from the onset of symptom to randomization as continuous variable
- Days from diagnosis to randomization as continuous variable

- Clinical status based on the 9-point ordinal scale (Score=0, 1, ...8)  
[REDACTED]
- Baseline PaO2/FiO2 as continuous variable
- Baseline PaO2/FiO2 category (<100 mm Hg, 100–200 mm Hg, > 200 -300 mm Hg, > 300 mm Hg)
- Marker for inflammation as continuous variables: CRP, Serum Ferritin, D-Dimer, LDH

#### **2.3.4 Medical history**

Any condition entered on the Medical History (MH) eCRF will be coded using the MedDRA dictionary. Relevant medical history and current medical conditions will be summarized by primary system organ class (SOC), preferred term (PT) and treatment group using the FAS.

The number and percentage of patients with the following comorbidities will also be summarized:

- Cerebrovascular disease
- Chronic heart disease
- Hypertension
- Diabetes
- Asthma
- COPD
- Chronic kidney disease
- Malignant neoplasm
- Liver disease

### **2.4 Treatments (study treatment, rescue medication, concomitant therapies, compliance)**

#### **2.4.1 Study treatment / compliance**

There is only a one-time treatment given on Day 1 of the study. The number and percent of patients discontinued from study treatment, i.e., with an interruption due to adverse event during the 2-hour infusion and never restart the study treatment, will be summarized by treatment arm. The duration from Day 1 to the end of safety follow up will also be summarized based on the Day 29 data cut.

#### **2.4.2 Prior, concomitant and post therapies**

Analyses described in this section will be performed on the safety set.

#### **2.4.2.1 Concomitant medication**

Records on the Prior and Concomitant Medications eCRF page will be coded using the WHO drug dictionary. All medications will be classified as prior or concomitant medication as follows:

- Prior medications are defined as drugs taken and stopped prior to start of the study medication on Day 1.
- Concomitant medications are defined as drugs taken at least once after the start of the study medication on Day 1

Medications will be categorized into one (and only one) of the two classes based on recorded or imputed start and end dates. When incomplete or missing, dates will be imputed according to Novartis standards ([Section 5.1.3](#)).

Medications in one of the two categories will be summarized separately by treatment group, ATC code (ATC class level 3, i.e., therapeutic/pharmacological subgroup) and preferred term.

#### **2.4.2.2 Surgical and medical procedures**

Records on the surgical and medical procedures eCRF page will be coded using the MedDRA dictionary. All procedures will be classified as prior or concomitant procedure, in the same way as done for concomitant medications. Surgical and medical procedures in one of the two categories will be summarized separately by SOC, PT and treatment group.

Imputation rules for start and end dates will follow the same rule as for the concomitant medications ([section 5.1.4](#)).

### **2.5 Analysis of the primary estimand**

The primary analysis for this study will be conducted on the FAS using treatment policy strategy.

#### **2.5.1 Primary estimand**

The primary clinical question of interest is: Does canakinumab + SoC increase the chance of survival without ever requiring invasive mechanical ventilation among patients with COVID-19-induced pneumonia and CRS after start of treatment, regardless of other subsequent clinical interventions?

The justification for this primary estimand is that it captures the clinical outcome of most interest after the canakinumab administration, which reflects also any effects of additional subsequent interventions potentially due to such clinical decision. In the ongoing COVID-19 pandemic with evolving treatment guidelines and healthcare system burdens, this primary estimand is deemed better to reflect actual clinical practices. In addition, the IV delivery of canakinumab is expected to result in a fast decrease in pharmacologically active IL-1 $\beta$  and to reduce IL-1 $\beta$  signaling to marginal levels within hours. However, clinical signs or symptoms within the 24 hours after treatment may not necessarily reflect such pharmacological effect yet. Therefore, only clinical status starting from Day 3 will be considered for the primary endpoint.

The primary estimand includes the following components:

Population: Patients with COVID-19-induced pneumonia and CRS.

**Endpoint:** Clinical response, defined as survival without ever requiring invasive mechanical ventilation (i.e., 9-point ordinal score $\geq 6$ ) from Day 3 (inclusive) up to day 29 (inclusive). A patient will be defined as a non-responder if the worst clinical status at any time from Day 3 (inclusive) up to Day 29 (inclusive) is requiring invasive mechanical ventilation or death (category 6, 7 or 8 on the WHO 9-point clinical status ordinary scale (Section 5.1)).

**Treatment of interest:** The randomized study treatment (canakinumab or placebo) added onto SoC with or without additional subsequent clinical interventions.

**Handling of intercurrent events:**

The treatment policy strategy will be adopted for primary analysis.

- Clinical interventions (e.g. mechanical ventilator, oxygen, intubation) newly administered as escalated SoCs corresponding to the progression of disease are integrated in efficacy evaluation based on the 9-category ordinal scale.
- Other new or change in strength of concomitant interventions will not be adjusted for primary analysis.
- Early discontinuation from study or lost to follow up before Day 29: A patient will be considered as responder if did not require invasive mechanical ventilation any time on or after Day 3 and meets at least one of the following two criteria:
  - The patient was discharged from hospital with clinical status of 0 or 1
  - The last clinical status was on Day 15 or later and better than baselinePatient will otherwise be considered as non-responder.

**Summary measure:** Odds-ratio comparing response rates in the canakinumab and placebo groups.

**2.5.2 Statistical hypothesis, model, and method of analysis**

The null hypothesis for the primary analysis is that there is no difference in the response rate

[figure not shown]
The numbers and percentages of responders will be summarized by treatment groups. The difference in observed response rates between canakinumab and placebo arms will also be presented along with the asymptotic 95% confidence interval.

### **2.5.3 Handling of missing values/censoring/discontinuations**

Missing data due to intercurrent events has been addressed via the handling of intercurrent event under the primary estimand definition.

The primary endpoint is based on clinical status starting from Day 3 (inclusive) post treatment. Patients who died or discontinued from study before Day 3 are excluded from the primary analysis. This is not expected to introduce a bias in favor of either treatment arm since the clinical status is not likely to be affected within two days by the study treatment administered on Day 1.

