#### **12.4.4 Handling of missing values not related to intercurrent event**

If a patient died first day after study treatment, the patient will be excluded from the primary analysis. Other missing data handling rules, if needed, will be specified in the SAP.

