**Document History – Changes compared to previous final version of SAP**

Date	Time point	Reason for update	Outcome for update	Section and title impacted (Current)
24-Apr-2020	Prior to FPFV	Creation of final version	First version	NA
17-Jun-2020				
		Added Hungary and Russia to the region of Europe		2.1 Data analysis general information
		Included misrandomized patients in the FAS per FDA request		2.2 Analysis sets and 5.4 Rule of exclusion criteria of analysis set
		Additional factors for subgroup analyses is added		2.2.1 Subgroup of interest
		The age categories for baseline summary have been updated to break $\geq 65$ years to 65-75 and $\geq 75$ Added baseline summary on PaO 2 /FiO 2 Deleted Chest x-ray or CT scan interstation since all patients will be abnormal at baseline		2.3 patient disposition, demographics and other baseline characteristics
		Added a supplementary estimand for the primary endpoint per FDA request Specified that early drop outs before Day 3 will be excluded from the analysis on the primary estimand		2.5 Analysis of the primary estimand

Date	Time point	Reason for update	Outcome for update	Section and title impacted (Current)
		Biomarker parameters will be summarized based on data with LOCF		2.7 Analysis of secondary efficacy objective(s)
		A summary on abnormal liver function parameters is added  Summary on SARS-CoV-2 virus test from central lab is added  Since the summary tables are added, the listings on the lab data and the virus testing results are deleted		2.8 Safety analysis
		[REDACTED]		[REDACTED]
		Other administrative updates and minor updates for clarifications		
16-Oct-2020	Before Day 29 DBL	Criteria for abnormal liver function parameters are updated per liver safety guidance	Amendment 2	2.8 Safety analysis

Date	Time point	Reason for update	Outcome for update	Section and title impacted (Current)
		[REDACTED]		[REDACTED]
		Updated the subgroups to align with the evolving SoC and data sharing request		Sections 2.2.1 and 2.9.1
		Other updates to clarify the previously specified analyses, to deal with unexpected data collection issues, or to address the review comments from Dry runs		Various sections
[REDACTED]	[REDACTED]	[REDACTED]	[REDACTED]	[REDACTED]

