### **2.5.4 Sensitivity analysis**

### **2.5.5 Supplementary analysis**

Two supplementary analysis will be conducted:

- An analysis will be conducted based on the definition for the primary estimand; however, all data from treatment up to Day 29 will be considered
- An analysis will be conducted based on data from Day 3 to Day 29 but by handling the discontinuation from study or lost to follow up on or before Day 29 as specified below:
  - A patient will be considered as responder if invasive mechanical ventilation is not required any time on or after Day 3 and the last clinical status returning to 0 or 1 before early discontinuation from study or lost to follow up
  - A patient with the last clinical status >1 before early discontinuation from study or lost to follow up will be considered as non-responder

The supplementary analyses will apply the same logistic regression model as for the primary estimand.

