### 2.6.1 Key secondary estimand

The key secondary clinical question of interest in this study is: Does the administration of canakinumab reduce 4-week mortality among patients with COVID-19-induced pneumonia and CRS, regardless of other subsequent clinical interventions?

The justification for this secondary estimand is that mortality currently represents the main epidemiological and clinical concern for COVID-19 patients and accumulating evidences suggest coexistence of CRS with severe COVID-19-induced pneumonia. Subsequent clinical interventions, including intensive care when a patient become terminally ill, reflect actual clinical practices, whose needs, scope and effectiveness could potentially be related to the earlier decision of canakinumab administration.

The key secondary estimand includes the following components:

Population: Hospitalized patients with COVID-19-induced pneumonia and CRS.

Endpoint: All COVID-19-related deaths (i.e., all deaths caused by study indication) during the 4-week period after study treatment

Treatment of interest: The randomized study treatment (canakinumab or placebo) added onto SOC with or without additional subsequent clinical interventions.

Handling of remaining intercurrent events:

The treatment policy strategy will be adopted for this key secondary analysis.

- Effect of other subsequent clinical interventions will not be adjusted
- Early study discontinuation or lost to follow-up before Day 29: a patient will be considered as survivor if the last clinical status of 0 or 1; otherwise, the patient will not be included in this key secondary analysis (note: this include deaths which are not marked as caused by study indication).

Summary measure: Odds-ratio comparing 4-week CFR in the canakinumab and control groups.

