Assuming the true response rate for the control arm lies within the range of 20% - 50%, a total sample size of 450 and 1:1 randomization ratio will provide at least 89% power to detect the minimum clinically meaningful benefit of interest.

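### The SAP drops deaths and discontinuations before Day 3 from the primary analysis, against its own full analysis set and the estimand's non-responder rule

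*SAP*

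**What the plan says.** **Population.** SAP 2.5: "The primary analysis for this study will be conducted on the FAS using treatment policy strategy". SAP 2.2 defines the full analysis set (FAS) as everyone randomised and adds: "Misrandomized patients will be included in FAS". SAP 5.4 lists missing consent as the only protocol deviation that removes a randomised patient.

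**Early discontinuation.** Protocol 2.1 and SAP 2.5.1 treat study discontinuation or loss to follow-up before Day 29 as an intercurrent event. The patient is a responder only if not invasively ventilated from Day 3 on and either discharged at status 0 or 1, or last assessed on Day 15 or later at a status better than baseline. Everyone else is a non-responder. Neither text sets an earliest day.

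**Exclusion.** SAP 2.5.3: "Patients who died or discontinued from study before Day 3 are excluded from the primary analysis". The reason given is that treatment on Day 1 is unlikely to affect clinical status within two days.

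**Protocol counterpart.** Protocol 12.4.4 is narrower: "If a patient died first day after study treatment, the patient will be excluded from the primary analysis". It leaves other missing-data rules to the SAP, in a section limited to values not related to an intercurrent event.

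**Declaration of changes.** The SAP document history records: "Specified that early drop outs before Day 3 will be excluded from the analysis on the primary estimand". SAP section 4, which lists departures from the protocol, reports none for the primary analysis.

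**Supplementary analyses (SAP 2.5.5).** The first keeps the primary definition; "however, all data from treatment up to Day 29 will be considered". The second covers Day 3 to Day 29 and scores discontinuations with last status above 1 as non-response. Neither says whether the 2.5.3 exclusion still applies.

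**The concern.** A patient who withdraws on Day 2 while on oxygen is a non-responder under SAP 2.5.1 and absent under SAP 2.5.3. Section 2.5.3 itself opens by saying that the estimand has already dealt with intercurrent events, then overrides the estimand for one of them.

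The endpoint is survival without invasive ventilation, yet deaths on Days 1–2 disappear from it. A patient intubated on Day 2 and still ventilated on Day 3 counts as a failure, while one who dies on Day 2 is not counted at all. The key secondary endpoint has no Day 3 start, being "All COVID-19-related deaths (i.e., all deaths caused by study indication) during the 4-week period after study treatment". A COVID-19 death on Day 2 is therefore an event there and missing from the primary analysis.

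The excluded patients are mostly failures on the endpoint. If early losses differ between arms, removing them favours the arm that had more. The rationale supports starting the scoring of ventilation at Day 3. It does not show that leaving the study is unrelated to treatment, and it does not justify removing deaths from a survival endpoint.

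**Working it through.** **1. The plan's power figure.** Inputs from Protocol 12.7.1 and SAP 3.1.1: 225 per arm, two-sided alpha 0.05, a 15-point benefit, control response 20–50%. With the pooled two-proportion formula,

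power = Φ{ [d√n − 1.96·√(2p̄(1−p̄))] / √(p₁(1−p₁) + p₂(1−p₂)) }.

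At 50% versus 65%: d√n = 0.15 × 15 = 2.25; p̄ = 0.575, so 1.96 × √0.48875 = 1.370; the denominator is √0.4775 = 0.691. Power = Φ(0.880/0.691) = Φ(1.273) = 89.9%. The other rows give 89.3%, 91.0% and 94.8%. The plan states 89%, 89%, 90% and 94%, so its figures reproduce. The problem is the analysis population, not the sample size.

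**2. False-benefit rate.** The loss rates are assumptions. Method: multinomial simulation, 400,000 trials per scenario, 225 per arm, unadjusted Wald test of the log odds ratio at two-sided 0.05. True response in the FAS is equal in both arms. The table gives the one-sided rate favouring canakinumab when early losses are excluded.

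| Early loss, canakinumab v placebo | 20% | 30% | 40% | 50% |
|---|---|---|---|---|
| 2% v 2% | 2.42% | 2.50% | 2.48% | 2.45% |
| 2% v 1% | 2.79% | 2.93% | 3.02% | 3.14% |
| 3% v 1% | 3.14% | 3.43% | 3.74% | 4.09% |

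Columns are the common FAS response rate. Across balanced losses of 1–5% the rate stays at about 2.4–2.5%. The unbalanced rows assume that canakinumab raises early loss and that a later effect offsets it exactly. If the drug does nothing, losses balance in expectation and the first row applies.

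**3. A single data set chosen to sit near 0.05.** Responders 109 v 90, early losses 5 v 1; SE = √(1/a + 1/b + 1/c + 1/d).

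- Excluded, 109/220 v 90/224: OR = (109 × 134)/(111 × 90) = 1.46, z = 0.380/0.192 = 1.98, p = 0.048.
- Counted as failures, 109/225 v 90/225: OR = (109 × 135)/(116 × 90) = 1.41, z = 0.343/0.191 = 1.80, p = 0.072.

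A smaller imbalance can also be enough. With 133 v 113 responders and losses of 2 v 0, the pooled z-test gives p = 0.045 with exclusion (133/223 v 113/225) and p = 0.058 without. Balanced losses of 5 v 5 in the same data give 0.055 against 0.058.

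**4. How often the two rules disagree.** With a true 15-point benefit and balanced early loss of 1–2%, they differ on significance in about 0.5–2.5% of simulated trials.

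**5. Power cost of keeping these patients (50% v 65%).** With loss f per arm, exclusion uses n = 225(1−f) and unchanged rates; counting as failures uses n = 225 and both rates multiplied by (1−f).

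| Loss per arm | Excluded | Counted as failures |
|---|---|---|
| 1% | 89.6% | 89.2% |
| 2% | 89.3% | 88.4% |
| 5% | 88.3% | 86.2% |

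**The case against.** The strongest reply is that little depends on this. With no treatment effect at all, error is not inflated. The raised rates need an early harm exactly offset later, a pattern no document supports. The 5 v 1 example is contrived: under balanced 1% loss, an excess of four or more losses on canakinumab arises in about 5% of trials, before a borderline p-value is also required. Early loss should be rare, because Protocol 5.2 excludes patients judged likely to die within 24 hours and Protocol 12.7.1 considers early discontinuation unlikely. Stopping the infusion is not study withdrawal (Protocol 9.1.1). These points stand, and they limit the size of the problem.

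It is also said that the rule is deliberate, explained, logged in the document history and made by a blinded team (Protocol 6.4), and that 2.5.3 is specific enough for a programmer to follow. That is largely fair. A specific rule that contradicts the estimand still leaves the estimand misdescribed, and the protocol's delegation does not reach discontinuation, which already has its own rule.

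The first supplementary analysis most naturally restores these patients. It does not carry the test, and its handling of the exclusion is not stated. The difference from the key secondary endpoint is not a contradiction in itself, since the windows differ; it only shows where the deaths go.

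The primary model and sensitivity text are redacted or not shown in the public copy, so nothing is inferred from them.

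**Conclusion.** The concern holds and should be fixed. The conflict is in the current text: the FAS with treatment policy and a non-responder rule without a lower day limit on one side, removal of deaths and discontinuations before Day 3 on the other. The SAP goes beyond the protocol's exclusion of first-day deaths, most clearly for discontinuations, and section 4 does not declare it. It also partly undoes the inclusion of misrandomised patients, because an untreated patient takes the randomisation date as Day 1 (SAP 2.1.1) and is dropped again if leaving before Day 3.

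The numerical effect is small: negligible if early losses balance, and up to about 4% one-sided in place of 2.5% if canakinumab has 2 points more early loss with equal overall response. All loss rates are assumed and the tests are unadjusted. The result would change only if it were close.

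**What to change.** - In the primary analysis, keep all FAS patients. Count any death through Day 29, including Days 1–2, as non-response. Apply the existing SAP 2.5.1 rule to discontinuations before Day 3. Keep the Day 3 start for ventilation status.
- Report the version with the exclusion as a sensitivity analysis.
- State in SAP 2.5.5 that both supplementary analyses include these patients.
- Reconcile Protocol 12.4.4 with SAP 2.5.1 and 2.5.3, and list the change in SAP section 4.

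The cost is SAP wording, a matching protocol correction and one derivation flag, with no new data. Response rates fall slightly in both arms, with the power loss shown above. Never-treated misrandomised patients who leave before Day 3 would count as non-responders unless they meet a responder criterion.

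If the sponsor prefers to keep the exclusion, the consistent alternative is to restate the estimand's population as patients alive and on study at Day 3 and to declare that in section 4. This removes the contradiction but leaves the primary test conditional on a post-randomisation event, so it is the weaker choice.
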